1.2 Analysis Sets

The analysis set in this surveillance is safety population. This analysis set is defined as described below.

- Safety population

In this document, the safety population is defined as all Leuplin PRO-treated patients evaluable for safety with no major protocol violation. Patients for whom the CRF has been collected will be excluded from the safety population if any of the following criteria is met:

- Not treated with Leuplin PRO
- Treatment before the contract period
- Registration 15 days or more after Leuplin PRO treatment
- It is unknown whether the patient experienced an AE
- Three-month depot administered

1.3 Number of Digits to be Displayed

- Percentage (%)

Proportion of patients with an AE or an ADR, etc. or number of AE or ADR, etc.:

Displayed to two decimal places by rounding

Other:

Displayed to one decimal place by rounding

- Summary statistics

Mean, median, first quartile, and third quartile:

Displayed to one lower digit than raw data by rounding

Standard deviation:

Displayed to two lower digits than raw data by rounding

Minimum and maximum:

Displayed to the same number of digits as the relevant data

1.4 Important Identified Risks, Important Potential Risks, and Important Missing Information

- Important identified risks
 - Injection site reaction: Injection site reaction is defined as the following AEs:
 - HLT code 10022097 [Infusion site reactions]
 - HLT code 10057196 [Administration site reactions NEC]
 - PT code: Refer to [Attached table 1 PTs corresponding to risks].
 - Decreased bone mass density: Decreased bone mass density is defined as the following AEs:
 - SMQ code 20000178 [Osteoporosis/osteopenia (SMQ) narrow]
 - PT code: Refer to [Attached table 1 PTs corresponding to risks].
 - Diabetes mellitus: Diabetes mellitus is defined as the following AEs:
 - SMQ code 20000041 [Hyperglycemia/new onset diabetes mellitus (SMQ) broad]
 - Interstitial lung disease : Interstitial lung disease is defined as the following AEs:
 - SMQ code 20000042 [Interstitial lung disease (SMQ) narrow]
 - Depression: Depression is defined as the following AEs:
 - SMQ code 20000167 [Depression (excl suicide and self injury) (SMQ) narrow]
 - SMQ code 20000037 [Suicide/self-injury (SMQ) narrow]
 - Thromboembolism: Thromboembolism is defined as the following AEs:
 - SMQ code 20000004 [Cardiac failure (SMQ) narrow]
 - SMQ code 20000166 [Conditions associated with central nervous system haemorrhages and cerebrovascular accidents (SMQ) narrow]
 - SMQ code 20000064 [Haemorrhagic cerebrovascular conditions (SMQ) narrow]
 - SMQ code 20000063 [Ischemic central nervous system vascular conditions (SMQ) narrow]
 - SMQ code 20000165 [Cerebrovascular disorders, not specified as haemorrhagic or ischaemic (SMQ) narrow]
 - SMQ code 20000082 [Embolic and thrombotic events, arterial (SMQ) narrow]
 - SMQ code 20000084 [Embolic and thrombotic events, venous (SMQ) narrow]
 - SMQ code 20000083 [Embolic and thrombotic events, vessel type unspecified and mixed arterial and venous (SMQ) narrow]
 - SMQ code 20000047 [Myocardial infarction (SMQ) broad]
 - SMQ code 20000168 [Other ischaemic heart disease (SMQ) broad]

- Pituitary apoplexy: Pituitary apoplexy is defined as the following AEs:
 - PT code: Refer to [Attached table 1 PTs corresponding to risks].
- Hepatic dysfunction/jaundice: Hepatic dysfunction/jaundice is defined as the following AEs:
 - SMQ code 20000009 [Cholestasis and jaundice of hepatic origin (SMQ) narrow]
 - SMQ code 20000013 [Hepatic failure, fibrosis, and cirrhosis and other liver damage-related conditions (SMQ) narrow]
 - SMQ code 20000010 [Hepatitis, non-infectious (SMQ) narrow]
 - SMQ code 20000008 [Liver related investigations, signs and symptoms (SMQ) narrow]
- Important potential risks
 - Anaphylaxis: Anaphylaxis is defined as the following AEs:
 - SMQ code 20000021 [Anaphylactic reaction (SMQ) narrow]
 - SMQ code 20000071 [Anaphylactic/anaphylactoid shock conditions (SMQ) narrow]
 - Hypertension: Hypertension is defined as the following AEs:
 - SMQ code 20000147 [Hypertension (SMQ) narrow]
- Important missing information: Not applicable

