3.2 Rationale

To evaluate potential effects of differences between Leuplin PRO and Leuplin SR, that is, difference amounts of leuprorelin acetate administered in a single dose and different time profiles of serum drug concentration after administration, on the safety, it was decided to investigate the occurrence of injection site reaction and other adverse drug reactions (ADRs) with an incidence of 1% or higher, including the time of onset, incidence, and seriousness.

The sample size of 300 patients was determined to detect ADRs with an incidence of 1% or higher at a probability of 95% or higher.

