5.0 Dosage and Administration

The usual adult dosage is 22.5 mg of leuprorelin acetate administered subcutaneously once every 24 weeks. Refer to the Precautions section of the package insert.

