9.5 Adverse Events (AEs)

1) Surveillance items

Presence or absence of injection site reaction, details of injection site reaction (specific symptom, date of onset, seriousness and reason for seriousness [refer to Table 2]), cause of discontinuation of Leuplin PRO treatment, intervention (presence or absence and contents), date of outcome assessment, outcome, causal relationship to Leuplin PRO [refer to Table 3]).

Presence or absence of AE other than injection site reaction (refer to Table 1), AE term, date of onset, seriousness and reason for seriousness (refer to Table

2), cause of discontinuation of Leuplin PRO treatment, intervention (presence or absence and name of the drug/intervention), date of outcome assessment, outcome, causal relationship to Leuplin PRO* (refer to Table 3)

Patients with “not resolved” or “unknown” outcome or “unevaluable” causal relationship should be followed up wherever possible.

* For the causal relationship to Leuplin PRO, the rationale for “not related” and the reason for “unevaluable” shall be collected.

Note) Additional points to consider for AEs

Abnormal worsening of target disease, for instance, worsening beyond the expected natural course of the disease, will be handled as an AE.

2) Time points of surveillance

Period from the start of Leuplin PRO treatment to 24 weeks after the start of treatment (or discontinuation of observation)

Table 1 Definition of adverse events

An AE is defined as any untoward medical occurrence in a clinical investigation subject administered a drug; it does not necessarily have to have a causal relationship with this treatment. An AE can therefore be any unfavorable or unintended sign (e.g., abnormal laboratory finding), symptom, or disease temporally associated with the use of a drug, whether or not it is considered related to the drug.

The following are also handled as AEs:

- Symptoms and so forth that occur in infants breast-fed by their mothers under treatment with a drug
- Untoward symptoms and so forth that occur in children treated with a drug
- Symptoms and so forth that occur as a result of occupational exposure to a drug
- Symptoms and so forth that occur after administration of counterfeit medicines of our ethical drugs
- Untoward symptoms that have become known to occur in drug users through lawsuits or other legal actions

Table 2 Criteria for assessing seriousness

An AE satisfying any of the following is assessed as serious:

1. Results in death (death)

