5.3 Occurrence of Injection Site Reaction Not Unrelated to Leuplin PRO

5.3.1 Occurrence of Injection Site Reaction Not Unrelated to Leuplin PRO

Patients included Safety population

in analysis:

Analysis item: Injection site reaction not unrelated to Leuplin PRO

Stratification factors: Specific symptom (multiple answers allowed) [Pain, pruritus, erythema, swelling, induration, abscess, ulcer, other]

Analysis methods: For the aforementioned analysis item, frequency tabulation will be performed in each stratum of the stratification factor.

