5.6 Summary of Patients in Post-Marketing Surveillance, etc. (Attachment Style 16)

Patients included Patients with the CRF collected

in analysis:

Analysis items: Patient number
Site name
Sex
Date of birth
Reason for use (disease code, disease name)
Concurrent illness (disease code, disease name)
Route of administration
Maximum dose
Mean dose
Units
Duration of use
Concomitant medication (NHI drug code, drug name)
Degree of response
ADR (disease code, disease name, outcome)
CRF number
Dropout

Analysis methods: The aforementioned analysis items will be listed in accordance with Notes 1 to 3 in Attachment style 16 in Notification concerning re-examination, PSEHB/PAB/ED Notification No. 1128-2 dated 28 November 2017.

Attached table 1 PTs corresponding to risks

Risk	PT code	PT
Injection site reaction	10022044	Injection site abscess
	10068791	Administration site abscess
Decreased bone mass density	10000397	Acetabulum fracture
	10002544	Ankle fracture
	10009245	Clavicle fracture
	10009506	Closed fracture manipulation
	10010149	Complicated fracture
	10010214	Compression fracture
	10014487	Elevation skull fracture
	10015741	External fixation of fracture
	10016042	Facial bones fracture
	10016450	Femoral neck fracture
	10016454	Femur fracture
	10016667	Fibula fracture
	10016970	Foot fracture
	10016997	Forearm fracture
	10017076	Fracture
	10017081	Fracture delayed union
	10017085	Fracture malunion
	10017088	Fracture nonunion
	10017107	Fracture of clavicle due to birth trauma
	10017290	Fractured ischium
	10017296	Fractured maxilla elevation
	10017308	Fractured sacrum
	10017310	Fractured skull depressed
	10018720	Greenstick fracture
	10019114	Hand fracture
	10020100	Hip fracture
	10020462	Humerus fracture
	10021343	Ilium fracture
	10022576	Internal fixation of fracture
	10023149	Jaw fracture
	10028200	Multiple fractures
	10030527	Open fracture

Risk	PT code	PT
	10030682	Open reduction of fracture
	10030684	Open reduction of spinal fracture
	10031290	Osteoporotic fracture
	10034122	Patella fracture
	10034156	Pathological fracture
	10037802	Radius fracture
	10039117	Rib fracture
	10039579	Scapula fracture
	10040960	Skull fractured base
	10041541	Spinal compression fracture
	10041569	Spinal fracture
	10042015	Sternal fracture
	10042212	Stress fracture
	10043827	Tibia fracture
	10045375	Ulna fracture
	10048049	Wrist fracture
	10049164	Fractured coccyx
	10049514	Traumatic fracture
	10049946	Cervical vertebral fracture
	10049947	Lumbar vertebral fracture

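### SAP 1.4 defines injection site reaction, for a subcutaneous product, by an HLT printed as infusion site reactions, and nothing reconciles that count with the CRF item

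*SAP*

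**What the plan says.** Protocol 5.0 gives the product as "22.5 mg of leuprorelin acetate administered subcutaneously once every 24 weeks". The sample-size rationale in Protocol 3.2 sets out to investigate "injection site reaction and other adverse drug reactions (ADRs) with an incidence of 1% or higher"; injection site reaction is the only reaction it names.

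Protocol 9.5 collects the reaction in its own CRF item, apart from all other AEs: "Presence or absence of injection site reaction, details of injection site reaction (specific symptom, date of onset, seriousness and reason for seriousness", followed by intervention, outcome and causality.

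SAP 1.4 lists injection site reaction first among the important identified risks and defines it by three components:

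- "HLT code 10022097 [Infusion site reactions"
- "HLT code 10057196 [Administration site reactions NEC"
- the PTs in Attached table 1, which for this risk are "Injection site abscess" and its administration-site counterpart.

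SAP 5.1.3 (all AEs), 5.1.5 (ADRs) and 5.5 (the Attachment Style 12 summary) all take the risk from 1.4. SAP 5.3.1 tabulates related injection site reactions by specific symptom: "Pain, pruritus, erythema, swelling, induration, abscess, ulcer, other". It does not cite 1.4. SAP 1.1 defines induration, the subject of 5.3.2 and 5.3.3, from the injection-site-reaction column of the CRF.

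**The concern.** Neither HLT in the definition carries an injection-site label, and the first is labelled for a route this product does not use. Either the code or the label is wrong, or the wrong group was chosen. The SAP does not say which of code and label governs. The sections on coding (Protocol 10.6, SAP 5.1.1 and 5.1.2) name MedDRA/J without a version, so a programmer cannot resolve the conflict from the plan.

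Also, the same clinical event reaches the report by two routes: a MedDRA grouping in 5.1.3, 5.1.5 and 5.5, and, it appears, the CRF item in 5.3. Section 1.4 does not mention the CRF item, 5.3.1 does not mention 1.4, and no step compares them. A fault in the grouping could therefore pass unnoticed.

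At stake are the risk-grouped tables, including the one for the regulator, for the reaction that the protocol singles out when it asks whether Leuplin PRO differs in safety from Leuplin SR.

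**Working it through.** **1. The plan's own figure.** Protocol 3.2 states 300 patients, to detect an ADR of 1% incidence with probability of at least 95%. The chance of at least one case is 1 − 0.99^300 = 0.951. The smallest sufficient N is ln(0.05)/ln(0.99), rounded up, which is 299. The stated figure reproduces, and this point does not dispute it.

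**2. Printed definition against CRF symptoms.**

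| Component in SAP 1.4 | Site named by its label | CRF symptoms explicitly covered at an injection site |
|---|---|---|
| HLT 10022097 | infusion | none |
| HLT 10057196 | administration, NEC | none |
| PT 10022044 | injection | abscess |
| PT 10068791 | administration | none |

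Read by label, pain, pruritus, erythema, swelling, induration and ulcer have no injection-site group. Some could still be counted if coded to an administration-site term.

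**3. Two readings.**

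- The label governs: 5.1.3, 5.1.5 and 5.5 count injection-site abscess plus anything coded to infusion-site or administration-site terms. Most injection site reactions could be left out.
- The code governs and denotes the injection-site group: the tables are right apart from events coded outside the listed groups. The loss is small or nil.

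Choosing between them needs the MedDRA/J dictionary, which is not among the documents.

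**4. Which tables can be compared.** SAP 5.1.3 counts AEs whatever their causality, while 5.3.1 counts only related ones, so these differ by design. SAP 5.1.5 and 5.5 count ADRs, which SAP 1.1 defines as all AEs except those judged not related; that is the causality filter of 5.3.1. The fair comparison is therefore 5.1.5 and 5.5 against the related CRF records.

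**5. Illustration only.** Let s be the share of injection site reactions that the 1.4 grouping captures. The documents give no value, so s is an assumption run over its whole range. For a true incidence of 1% and N = 300, the chance that the risk tables count at least one case is 1 − (1 − 0.01s)^300. The second row assumes a 5% incidence, which the documents do not give either; the expected count is 300 × 0.05 × s.

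| s | 1 | 0.9 | 0.75 | 0.5 | 0.25 | 0 |
|---|---|---|---|---|---|---|
| Chance of at least one counted, 1% incidence | 95.1% | 93.4% | 89.5% | 77.8% | 52.8% | 0% |
| Expected patients counted, 5% incidence | 15 | 13.5 | 11.25 | 7.5 | 3.75 | 0 |

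The table shows how the result depends on s. It does not estimate a loss.

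**The case against.** The strongest reply is that tabulation programs normally select by code, so the bracketed text may be no more than a slip. The SAP gives some support. The risk is headed injection site reaction, and Attached table 1 adds one injection-site and one administration-site abscess PT. That pairing fits an injection-site HLT beside the administration-site HLT, and no infusion-site abscess PT is added. There are similar slips elsewhere: one disease-status category is called premenopausal in 5.4.6 but preoperative in 3.1 and 5.4.1, and the outcome list in 5.2.1 has the unknown category twice. This stands as a hint, but it does not settle the code.

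It also stands that no reaction would vanish from the report. SAP 5.1.1, 5.1.2 and 5.2 tabulate every AE and ADR by SOC and PT, and 5.3.1 gives symptom detail. Only the risk-grouped tables are exposed.

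A reader might go further in three ways that the documents do not support:

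- **That the counts will disagree with 5.3.** If the code is right they could agree. SAP 5.3.1 is a symptom table with multiple answers allowed and specifies no overall incidence. Only induration is expressly tied to the CRF column; that 5.3.1 uses the same item is a reasonable inference from its symptom list.
- **That the hand-added abscess PTs prove the HLTs incomplete for other symptoms.** They suggest that abscess needed adding and show nothing about ulcer or the rest.
- **That a definite number of patients would be lost.** Multiplying 300 by an assumed incidence gives all assumed reactors, not those missed.

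Redefining the risk as CRF item or coded groups would also be debatable. Every other risk in 1.4 is defined in MedDRA terms, and Protocol 10.6.1 takes these events from the risk management plan, which is not available here.

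**Conclusion.** The point holds in limited form. As printed, the definition of the first-listed identified risk names a reaction group that does not match the route of administration, and it feeds 5.1.3, 5.1.5 and 5.5. The consequence ranges from a wrong label with little or no loss, if the code denotes the injection-site group, to risk tables that omit most injection site reactions, if the label governs. The documents do not allow a choice between these, and no undercount can be computed from them. The planned 300 patients and the 95.1% detection probability are unaffected.

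The missing check between the MedDRA count and the CRF item stands under either reading. It makes disagreement possible, not certain. The correction is worth making because the definition is operative, the reaction is central to the surveillance's question, and the remedy is cheap.

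**What to change.** 1. Check code 10022097 against its label in the MedDRA/J version used for coding. Correct SAP 1.4 so that code and label both name the injection-site HLT, and state that version.
2. Keep the risk definition in MedDRA terms.
3. State in 5.3.1 that it uses the CRF injection-site-reaction item.
4. Add a listing that reconciles related CRF-reported injection site reactions with those counted in 5.1.5 and 5.5, showing each event captured by only one source.

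The cost is one SAP correction and one extra listing. No new data are needed and the sample size does not change.

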1.5 Other Handling

- Time of onset of AE (or ADR, etc.): Time of onset of AE (or ADR, etc.) will be calculated as date of onset of AE (or ADR, etc.) - start date of Leuplin PRO treatment + 1. If the day of AE (or ADR, etc.) is unknown, 1 will be used for calculation. If an AE (or ADR, etc.) occurs in the same year and month as Leuplin PRO treatment is started, the start date of Leuplin PRO treatment will be used for calculation.
- Premenopausal breast cancer drugs other than LH-RH agonists and premenopausal breast cancer drugs other than Leuplin PRO will be classified using drug codes according to Attached table 2.

2 Number of Surveillance Medical Institutions, Number of Enrolled Patients, and Patient Composition

2.1 Disposition of Patients

Patients included All enrolled patients (enrolled patients)

in analysis:

Analysis items: Enrolled patients

Number of surveillance medical institutions

Patients with no CRF collected

Reason for failure to collect

[Transfer of the investigator, medical reason for the investigator, other]

Patients with the CRF collected

Non-finalized patients

Finalized patients

Patients excluded from safety evaluation*

Reason for exclusion (multiple tabulation)

[Not treated with Leuplin PRO, treatment before the contract period, registration 15 days or more after Leuplin PRO treatment, it is unknown whether the patient experienced an AE, 3-month depot administered]

Patients included in safety evaluation*

Analysis methods:

For the aforementioned analysis items, analysis will be performed as described below, and a patient composition diagram will be prepared.

For enrolled patients, the number of surveillance medical institutions will also be calculated. One medical institution with different departments will be counted as one medical institution.

* Patients included in safety evaluation refer to the safety population, and patients excluded from safety evaluation refer to patients excluded from the safety population (finalized patients excluded from the safety population here).

(1) Frequency tabulation

3 Patient Baseline Characteristics

3.1 Patient Baseline Characteristics

Patients included Safety population

in analysis:

Analysis items:	Age (years)	[<35 years, >=35 years, unknown]
	Time from diagnosis of premenopausal breast cancer to patient registration (months)	
	ECOG Performance Status	[0, 1, 2, 3, 4]
	Disease status	[Patient on preoperative adjuvant therapy, patient on postoperative adjuvant therapy, patient with advanced breast cancer, patient with recurrent breast cancer]
	Presence or absence of hormone receptor expression	[No, yes, unknown]
	Diagnostic category	[Outpatient, inpatient]
	Presence or absence of predisposition to hypersensitivity	[No, yes, unknown]
	Presence or absence of concurrent illness	[No, yes]
	Detail of concurrent illness (multiple tabulation)	[Lifestyle diseases, hepatic disease, renal disease, allergic disease, malignant tumor, other]
	Presence or absence of history of thromboembolism	[No, yes, unknown]
	Detailed history of thromboembolism (multiple tabulation)	[Myocardial infarction, cerebral infarction, venous thrombosis, pulmonary embolism, other]
	Height (cm)	
	Body weight (kg)	
	BMI (kg/m ²)	[<18.5, 18.5-<25.0, 25.0-<30.0, >=30.0, unknown]
	Presence or absence of treatment with LH-RH agonist immediately before the start of Leuplin PRO treatment	[No, yes]

Disposition of treatment with LH-RH agonist immediately before the start of Leuplin PRO treatment	[Leuprorelin acetate 3.75 mg, leuprorelin acetate 11.25 mg, goserelin 3.6 mg, goserelin 10.8 mg]
Presence or absence of treatment with premenopausal breast cancer drug other than LH-RH agonists immediately before the start of Leuplin PRO treatment	[No, yes]
Disposition of treatment with premenopausal breast cancer drug other than LH-RH agonists immediately before the start of Leuplin PRO treatment (multiple tabulation)	[Adrenal hormone preparations, estrogen and gestagen preparations, oral anti-renal anemia agents/anti-mammary tumor agents, bone resorption inhibitors, alkylating agents, antimetabolic agents, antitumor antibiotics and preparations, antineoplastic preparations extracted from plants, antineoplastic agents]

Analysis methods: For the aforementioned analysis items, frequency tabulation will be performed for discrete data, and summary statistics will be calculated for continuous data.

4 Treatment Given

4.1 Treatment Status of Premenopausal Breast Cancer Drug Other Than Leuplin PRO

Patients included Safety population

in analysis:

Analysis items:	Presence or absence of treatment with premenopausal breast cancer drug other than Leuplin PRO	[No, yes]
	Disposition of treatment with premenopausal breast cancer drug other than Leuplin PRO (multiple tabulation)	[Adrenal hormone preparations, estrogen and gestagen preparations, oral anti-renal anemia agents/anti-mammary tumor agents, bone resorption inhibitors, alkylating agents, antimetabolic agents, antitumor antibiotics and preparations, antineoplastic preparations extracted from plants, antineoplastic agents]

Analysis methods: For the aforementioned analysis items, frequency tabulation will be performed.

